MedStar Diabetes Pathway Ongoing Chart Review Protocol

[name] Principal Investigator

Sub-Investigators

[name] [name]

[name], CRNP, CDE

[name], CRNP

[name]

[name], MS, RD, CDE and [name], MS, RD, CDE
Program Managers

June 1.2016

MedStar Diabetes Pathway Ongoing Chart Reviews

I- Background.

The MedStar Diabetes Pathway (MDP) early pilot program has generated evidence that an innovative technology-enabled “Boot Camp” approach to the delivery of diabetes survival skills education and medication management has a significant impact on glycemic control and healthcare utilization measures. The MDP is a 12 week Diabetes “Boot Camp” technology-enabled intervention which will offer learner-centered survival skills self-management education (DSSE) and algorithm-driven diabetes medications (DM) titration by Endocrinologist-supervised Certified Diabetes Educators (CDE), NPs and PharmDs. The program has been offered at 5 MedStar Medical Group (MMG) Primary Care Practices in FY 15-16 to high risk adults with uncontrolled type 2 diabetes who have a hemoglobin A1C (A1C) level -a marker of average blood glucose (BG) levels in the 2-3 months prior to the time the test is done- which is at or above 9% - considered to be poor control, and 1 or more additional risk factors for poor health outcomes. The program has been well received by MedStar Primary Care Providers and their diabetes patients.

Patients who consent to join the program attend two 1:1 visits with a CDE followed by “virtual” visits via telephone/texting. DSSE is tailored to baseline DM knowledge and medication adherence deficits. An FDA cleared cellular-enabled blood glucose (BG) monitoring system (Telcare BGM®) auto- transmits BGs to a provider dashboard in near-real-time. The CDE reviews BGs and contacts patients at minimum weekly to discuss and make adjustments to DM medications and/or lifestyle, until BG targets are reached. The patient then returns to his/her Primary Care Provider (PCP) with any further ongoing DM management recommendations.

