Ninety-eight (98) patients with uncontrolled type 2 diabetes have completed the MedStar Diabetes Pathway Boot Camp. A1C, a measure of average blood glucose control over the 2-3 months prior to the test being done, was checked at baseline and then after 3 months follow-up. Admissions and resource utilizations were measured for the period 6 months before baseline and then recorded between baseline and 3 months and between 3 months and 6 months. For comparison of A1C improvement, patients were matched to controls at a 1:3 ratio on age, sex, race/ethnicity, insurance group, and baseline A1C. The difference in improvements of A1c between a case and its matched control was tested. Utilization has not yet been captured for controls.

Clinical and Health Resources Utilization Outcomes.

- **A1C Performance.**

Blood glucose control improvement, as measured by change in A1C results is shown below.

Table 1: Change in A1C

	Boot Camp Cases	Control Cases	P value
Baseline A1C (%)	11.35 (1.86)	11.41 (1.71)	0.439
3 month A1C (%)	8.31 (1.52)	9.77 (1.98)	<0.001
Change in A1C (%)	-3.08 (2.01)	-1.64 (1.97)	<0.001
Percent A1C lowering	27%	14%	

The 3.08 % lowering of A1C among Boot Camp patients is highly clinically important. In comparison, most drug trials where A1C lowering is measured, there is typically reduction in A1C of 0.5-1.5% depending upon the drug or drugs being tested¹. Furthermore, a 1% absolute reduction in A1C can be correlated with an approximately 15% reduction in risk for myocardial infarction². The fact that lowering in A1C was also seen among control cases is not completely unanticipated. Per current standard care, when a patient presents with a markedly elevated A1C the physician caring for him/her would implement measures to help improve control which explains the concurrent fall in A1C over time. These results show that the Boot Camp intervention effectively doubled A1C lowering when compared to controls.

- **Health Resource Utilizations.**

Utilization for urgent care visits, urgent PCP visits, hospitalizations, and Emergency Department (ED) visits due to diabetes, taken in the 6 months before the listed time is shown in Table 2.

Table 2. Health Resource Utilizations

	Baseline (n)	3 months		6 months		P value
	Number	Number	% Reduction	Number	% Reduction	
Urgent Care Visits	3	0		0		0.109
Urgent PCP Visits	13	1	91%	1	92%	0.002
Hospitalizations	9	1	88%	3	66%	0.207
ED Visits	18	1	94%	2	88%	<0.001

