There is an association between time and urgent PCP visits and ED visits. This means that for those patients enrolled in the program there appears to be a reduction over time in urgent PCP visits and ER visits following program completion. The number of hospitalizations was low overall and does show a trend for reduction over time.

Summary of Findings.

This pilot evidence demonstrates a significant impact on glycemic control and healthcare utilization measures as the result of a concise, focused DM education and medication management intervention.

Phase 2.0 MedStar Diabetes Pathway Expanded Pilot

Building on the success of the MDP Phase 1.0 pilot, the next steps in expanding the program will be as follows:

- **Transition** of the Pathway from early feasibility pilot to the next phase as an expanded pilot program integrated within the MedStar Health System care delivery network and built upon a sustainable infrastructure (brick and mortar –plus- virtual components) across early adopter MMG practice sites.
- **Expand recruitment** to include high risk patients with uncontrolled type 2 diabetes, including those with a new diagnosis and A1C >9%, who have MedStar Emergency Department and/or Inpatient encounters
- **Spread** to additional targeted MedStar Medical Group (A&B) Primary Care Practices and/or to MedStar Managed Care Plan participants (MedStar Family Choice, MedStar Select)

As the MDP is transitioning into a clinical program offered at various MedStar sites, the MDP clinical team is reviewing the data collected during the pilot to improve the program and adapt it to various clinical settings in order to better serve the target patient population. It will be imperative to continue reviewing patient clinical outcomes as the program expands in order to insure continuous quality improvement of the program. This will be achieved through chart reviews of patients receiving diabetes care via the MDP.

III- Chart Review and Data Collection

MDP patients' chart review:

MDP target population:

Inclusion Criteria

- Active and established patient of a MedStar Medical Group Ambulatory Primary Care practice provider:
- Diagnosis of type 2 diabetes on EMR problem list for ≥ 1 year
- New diagnosis of type 2 diabetes with $A1C \geq 9$
- Active practice patient as evidenced by one or more visits to PCP in the past 12 months
- Age ≥ 21 to < 75 years
- $A1C \geq 9.0\%$ at their last visit to MedStar Medical Home, ED or hospital admission.

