- Primary Care Provider willing to have patient enter the program
- Patient is able and willing to participate in the program
- Proficient in English

-AND- one or more of the following high risk characteristics:

- Acute care encounter(s) including) ED visit(s) or hospital admission(s) in the past year with uncontrolled diabetes (BG > 200mg/dL or A1C >9%; severe hypoglycemia = BG <40mg/dL requiring assistance to treat)
- Evidence of low medication adherence as evidenced by no refills since one or more prescribed DM RXs “ran out” (based on last Rx for each DM med and time period was prescribed for on EMR/SureScripts medications list); or any other circumstance that has

been identified by the health care team which indicates poor adherence to prescribed medication.

- Does not meet HEDIS diabetes measures for two or more of: no MA/Cr, no DM retinal exam, no lipid profile
- SBP \geq 140 mmHg
- LDL \geq 100 mg/dL
- Depression diagnosis on problem list (*or depression medication on med list*)
- BMI >32

Exclusion Criteria

- Known history of DKA
- No MedStar PCP visit within past 12 months
- Endocrine or Diabetes Education consult referral order in the past 6 months which resulted in Endo visit(s) or DSME visit(s) documented in chart or self-reported by patient during initial screen
- Active additional medical issues which in the opinion of the care team would preclude concentrating on BG control and/or would predispose to ED visits and/or hospital admits independent of glycemic control, e.g.: severe CHF, severe COPD; severe mental illness.
- Resident of skilled nursing facility, nursing home or receiving home health care services.
- Active cancer in the preceding 3 years excluding nonmalignant basal cell cancer
- Supraphysiologic doses of glucocorticoids (hydrocortisone > 30mg/day; prednisone > 5-6mg daily; dexamethasone > 2mg daily).
- Pregnant or anticipates attempting conception in the following year
- Patient and/or custodial caregiver unwilling and/or unable to participate in program-related activities

The following data will be collected retrospectively from the charts of patients that complete the MDP.

- Demographics
- A1C baseline, at 3 month after baseline visit to assess impact of the pathway.
- Hypoglycemic events (BG<70 and <40) during the 6 months of enrollment in MDP
- Diabetes 2 go Knowledge test
- ED and hospital visits in 30 days and 90 days prior to and after the boot camp
- Referring MedStar Provider satisfaction with intervention

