- Patient satisfaction with the MDP

In addition, the clinical team will also compare the clinical and utilization outcomes of patients enrolled in the MDP with those of a randomly selected control group consisting of MedStar

patients with elevated A1C levels. This will be done to allow a better assessment of the impact and effectiveness of the MDP.

Once the data is obtained, it will be de-identified prior to data analysis and reporting. Demographics will be reported as a group, i.e. percentage of patients within a certain age group or geographic area or with a certain type of insurance to insure equal access to the MDP, and help recruit underrepresented groups so they can also benefit from the program.

Data Management

The MedStar Health Research Institute will provide data management services for all aspects of the chart review process, including preparation of the program REDCap database, quality checks of data and developing processes for bringing data into REDCap from available data sources held by system partners which will be leveraged for the program. All data will be de-identified prior to presentation to the Biostatistician for analysis.

Data Analysis and Reporting Plan

Data analysis will be performed by the MHRI Biostatistician. All data will be de-identified prior to submission to the biostatistician for analysis. Results will be reviewed for quality improvement purposes and will also be presented at national meetings. Additionally, one or more manuscripts will be prepared for submission to peer-reviewed journals.

References

1- Management of Hyperglycemia in Type 2 Diabetes: A Patient-Centered Approach

Position Statement of the American Diabetes Association (ADA) and the European Association for the Study of Diabetes (EASD). [Silvio E. Inzucchi](#), MD,¹ [Richard M. Bergenstal](#), MD,² [John B. Buse](#), MD, PHD,³ [Michaela Diamant](#), MD, PHD,⁴ [Ele Ferrannini](#), MD,⁵ [Michael Nauck](#), MD,⁶ [Anne L. Peters](#), MD,⁷ [Apostolos Tsapas](#), MD, PHD,⁸ [Richard Wender](#), MD,⁹ and [David R. Matthews](#). Diabetes Care. 2012 Jun; 35(6): 1364–1379.

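### Outcome data are listed only for patients who complete the programme, but the controlled comparison is described as one of enrolled patients; completion and the analysis set are undefined

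*Protocol*

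**What the plan says.** The documents describe the programme arm in several ways.

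- **Protocol, section III, data to be collected.** The list is introduced by "The following data will be collected retrospectively from the charts of patients that complete the MDP". It covers A1C, hypoglycaemia, a knowledge test, satisfaction, and "ED and hospital visits in 30 days and 90 days prior to and after the boot camp".
- **Protocol, section III, comparison with controls.** The team will "compare the clinical and utilization outcomes of patients enrolled in the MDP" with those of randomly selected MedStar patients with raised A1C, in order to judge the programme's effectiveness. No completion, retention or follow-up rule is stated for the controls.
- **Protocol, end of the Phase 2.0 section.** The review is said to cover charts of patients receiving care through the programme. That is broader than completers, but no data items are attached to it.
- **Protocol, Background (pilot).** The results come from 98 "patients with uncontrolled type 2 diabetes have completed the MedStar Diabetes Pathway Boot Camp", with no number enrolled. The utilization summary speaks of "those patients enrolled in the program there appears to be a reduction over time in urgent PCP visits and ER visits following program completion", using both terms for the same people. The only matching variables listed anywhere are the pilot's: "patients were matched to controls at a 1:3 ratio on age, sex, race/ethnicity, insurance group, and baseline A1C".
- **SAP.** It refers to participants and to the intervention group. It names no analysis set and gives no rule for non-completers or missing A1C. The adjusted Poisson models use pre-intervention utilization, baseline HbA1c, age and sex.

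Completion is not defined. The Background gives a fixed length ("The MDP is a 12 week Diabetes" boot camp). It also says that contact continues until glucose targets are met, after which the patient returns to primary care. The section III list mentions a six-month enrolment period.

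**The concern.** Finishing the programme happens after baseline and is plausibly related to how well a patient does. If only finishers' charts are abstracted, the programme arm is selected on that event while the controls face no stated equivalent. The pilot matching variables and the SAP covariates are all measured before the intervention, so they cannot remove such selection.

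The two kinds of outcome are affected differently. An A1C change score needs a follow-up A1C in both arms, so controls are partly selected as well; how strongly is unknown. ED and hospital visits need no follow-up test, so for them the programme arm's selection has no counterpart. The modelled 90-day hospitalization figure also feeds the SAP's annual cost projection, so the choice of patients carries into that result.

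The protocol plans publication and an assessment of effectiveness. Readers would need to know whether the estimate describes those who finished or those who were enrolled.

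**Working it through.** **The plan's own figure.** The SAP gives a difference of 0.5, SD 2, 80% power, alpha 0.05 and 128 per group with a paired t-test. With a noncentral t and a two-sided test (sidedness is not stated), 128 pairs give 80.15% power. The figure reproduces, so the issue is who is analysed and not the sample-size arithmetic.

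**Inputs.** Protocol Table 1: A1C change of -3.08 (SD 2.01) in cases and -1.64 (SD 1.97) in controls, so the difference is 3.08 - 1.64 = 1.44. SAP observed difference: 1.6 (SD 2.25). The non-completion fraction d appears nowhere; 10, 20 and 30% are assumptions.

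**Pilot difference among all enrolled**, treating 3.08 as the completers' change:

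| Assumption about non-completers | Formula | d = 10% | 20% | 30% |
|---|---|---|---|---|
| Changed like controls | 1.44 × (1 - d) | 1.30 | 1.15 | 1.01 |
| Did not change | 3.08 × (1 - d) - 1.64 | 1.13 | 0.82 | 0.52 |

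The first row is not bias. It is a different estimand: the effect in everyone enrolled rather than in finishers. The second row is lower by a further 1.64 × d = 0.16, 0.33 and 0.49, because non-completers are there assumed to do worse than untreated controls.

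**Selection with no programme effect.** Assume a latent normal completion propensity that has correlation rho with A1C improvement, improvement SD 2, and unselected controls. The false advantage is

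b = rho × 2 × phi(z) / (1 - d), with z = Phi⁻¹(d).

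The factor phi(z)/(1 - d) is 0.195, 0.350 and 0.497 at d = 10, 20 and 30%. At rho = 0.3, b = 0.12, 0.21 and 0.30. With 128 pairs, SD of the paired difference 2 and two-sided alpha 0.05, a false difference of that size would be significant in about 10, 22 and 39% of studies.

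Here rho is the correlation with the latent propensity, not with completion as a yes/no variable. For the latter the formula is rho × 2 × √(d/(1 - d)), which gives 0.20, 0.30 and 0.39 at rho = 0.3. The two scales must not be mixed.

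**Upper limit.** At rho = 1 on the latent scale and d = 30%, b = 2 × 0.497 = 0.99. That would leave 1.6 - 0.99 = 0.61 of the SAP difference and 1.44 - 0.99 = 0.45 of the pilot difference.

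**ED and hospital visits.** The documents give no basis for a comparable figure, so none is offered.

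**The case against.** The strongest reply is that this is loose wording. The comparison paragraph names its own population (enrolled), the Phase 2.0 text is broader than completers, and the pilot summary uses both terms for one group. In a retrospective review, completing may mean only that the programme period has passed. This stands in part: a deliberate completer-only design cannot be inferred. But the section III list is the only instruction on what to abstract. Followed as written, it yields no data for an all-enrolled analysis.

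A reader might infer that only the programme arm is conditioned on a post-baseline event. The documents do not support that for A1C, because controls need a follow-up value to have a change score. The asymmetry is clear only for utilization and cost.

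A reader might also take completion to mean reaching glucose targets, which would select patients directly on response. The Background text permits that reading but does not establish it.

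Finally, the calculations rest on assumptions. No change at all in non-completers is a harsh one, since the protocol attributes the controls' fall of 1.64 to standard care, which non-completers could also receive. The selection model leaves controls unselected, which overstates the asymmetry for A1C. Both criticisms stand, and the figures are illustrations only.

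**Conclusion.** The point holds as an unresolved definition with a possible selection effect. The documents use completers, enrolled patients, patients receiving care and participants without reconciling them. They define neither completion nor an analysis set, and they list no data for non-completers. Taken literally, the programme arm is selected after baseline. Controls are partly selected for A1C change and not at all for ED visits, hospital visits and the cost projection.

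The direction plausibly favours the programme but is not proven. The size is unknown because no enrolled count is given. A reader might conclude that the reported A1C benefit is an artefact; that does not follow. At up to 30% non-completion, even the extreme of the selection model (0.99) is below both 1.44 and 1.6. Nor do the documents say that the SAP's 1.6 comes from completers. What is at stake is the size and meaning of the estimate. Correcting this is a cheap improvement.

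**What to change.** 1. In the section III data list, replace the restriction to completers with all patients enrolled in the programme, meaning those who consented to join. Use that set as the main comparison in section III and the SAP. Report completers as a labelled secondary analysis.
2. Define completion for analysis, and report the numbers enrolled, completed and analysed.
3. Use the same 3-month A1C window for cases and controls. Handle missing 3-month values by a repeated-measures mixed model of baseline and 3-month A1C, or by multiple imputation. A mixed model of change scores would not do, because it drops patients with a missing change. Add one sensitivity analysis in which cases with missing A1C take their matched controls' change.
4. For utilization, keep the 30- and 90-day lengths but put everyone on one clock. The pre-window ends at the baseline or index date, and the post-window starts a fixed 12 weeks after it, for completers, non-completers and matched controls alike. Assign dates by the same written rule to enrolled patients who never attend.
5. State as a limitation that entry already requires "Patient is able and willing to participate in the program", so some selection on engagement remains in the all-enrolled comparison.

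The cost is a wording change in both documents and abstraction of further charts from the same record system. Because the SAP is written in the past tense, a re-analysis may be needed. There will be some missing A1C values, an assigned rather than actual programme end date, and probably a smaller estimated effect.

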Statistical Analysis for the MedStar Diabetes Pathway Ongoing Chart Review Protocol. (June 1, 2016).

The study was powered to detect a difference of 0.5 in the change in HbA_{1c} with SD=2 with 80% power at alpha=0.05 with a sample size of 128 in each group (paired t-test). The study reaches 100% power to detect this observed difference (1.6, SD=2.25, post-hoc) with an alpha level of 0.01. Data were summarized using means and standard deviations for continuous variables and frequencies and percentages for categorical variables. Differences in patient characteristics and the unadjusted differences in the outcome measures between the intervention and control groups were tested using linear mixed models, McNemar tests, and conditional logistic models due to matching (Tables 2 and 3). The significance of the comparison between the groups of their respective within group risk change from pre to post-intervention was determined by longitudinal Poisson models that include time and group interactions. Multivariable Poisson regression models adjusted for pre-intervention utilization, baseline HbA_{1c}, age, and sex were used to estimate post-intervention 30-day and 90-day hospital admission and ED visit risk for participants compared to controls (Table 3). The average decrease in HbA_{1c} among men compared to women was examined using a mixed model that included an interaction with sex and group.

Pre-intervention differences between the groups in utilization outcomes were computed and tested using unadjusted Poisson regression models. Analyses were conducted in R 3.1.0 (R Core, Vienna, Austria) (31) and Stata 14 (StataCorp, College Station, TX) (32).

We also conducted an analysis to examine potential for monetization of the intervention benefits from reduced inpatient services to the health system. Based on the expected times of hospitalization per patient in 90 days for both the intervention group and comparison group, estimated by the Poisson regression model, we projected the annual difference in usage of inpatient services between a patient with and without the intervention. The projected change in usage was then multiplied by the expense per diabetes associated hospitalization, which was calculated from the actual claims data of the health system's employee health plan in Year 2017 to be \$25,162.95 per hospitalization.

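### No A1C before baseline is collected, so regression to the mean that differs between programme patients and controls can be neither detected nor reduced

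*Protocol*

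**What the plan says.** **Programme patients.** Under Inclusion Criteria (Protocol, section III), a patient needs an A1C of at least 9.0% "at their last visit to MedStar Medical Home, ED or hospital admission". No second or confirming value is required. The patient must also have at least one of seven high-risk features: an acute encounter with uncontrolled diabetes, low medication adherence, missed HEDIS measures, raised systolic pressure, raised LDL, depression, or BMI above 32.

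**Controls.** For the ongoing review, section III describes a "randomly selected control group consisting of MedStar" patients with elevated A1C. It gives no threshold, care setting, index date or A1C history. In the pilot (section I), cases were "matched to controls at a 1:3 ratio on age, sex, race/ethnicity, insurance group, and baseline A1C". The SAP says that group differences "were tested using linear mixed models, McNemar tests, and conditional logistic models due to matching", but does not name the matching variables.

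**A1C data.** The list in section III has "A1C baseline, at 3 month after baseline visit to assess impact of the pathway". No earlier A1C is listed, and no SAP model contains one. Baseline HbA1c enters the adjusted Poisson models for utilisation. The HbA1c comparison is described as unadjusted, apart from a sex-by-group interaction model.

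**Fall in controls.** Below Table 1, the Protocol says that physicians act on a markedly raised A1C, "which explains the concurrent fall in A1C over time". Regression to the mean is not mentioned.

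**The concern.** A group chosen for a high A1C will on average read lower later, whatever is done. A control group removes that fall from the comparison if both groups would have regressed equally. Matching on one baseline value does not guarantee this. Take two patients at 11%, one from a population that usually runs near 9% and one from a population that usually runs near 10%. Their expected later values differ even with no programme.

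The design leaves room for such a difference. Programme patients may qualify at an ED visit or admission, and the Phase 2.0 section deliberately adds ED, inpatient and newly diagnosed patients. The setting of the controls' A1C is not stated. If programme patients have the lower usual level, the bias favours the programme; if they are chronically higher, it works against it. It could also work against the programme if their baseline is re-measured at the first visit while the controls' baseline is the qualifying value.

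The plan treats its two outcomes differently. For utilisation it collects a pre-programme period and adjusts for it. For HbA1c, the outcome that the study is powered on, it has nothing before baseline with which to check comparability.

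**Working it through.** **1. The plan's own figure.** Inputs from the SAP: difference 0.5, SD 2, 80% power, alpha 0.05, paired t-test. The normal approximation gives ((1.960 + 0.842) × 2 / 0.5)² = 125.6. The exact two-sided paired t calculation gives 128 pairs, with 80.2% power. The stated 128 is reproduced, and nothing below changes it.

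**2. Form of the bias.** Suppose that, without any programme effect, expected follow-up in group g is μ_g + b × (baseline − μ_g), where μ_g is the group's usual mean A1C and b is the slope of follow-up on baseline. At the same baseline the two groups then differ by

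bias = (1 − b) × (μ_MDP − μ_control).

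The second factor is the difference in overall usual means, not the difference among patients who share a baseline value.

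**3. Size.** Neither factor is in the documents. Assume 1 − b from 0.3 to 0.7 and a difference in usual means of 0.5 to 1.0 point:

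- smallest: 0.3 × 0.5 = 0.15 points
- largest: 0.7 × 1.0 = 0.70 points

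**4. What Table 1 says about the slope.** The correlation follows from the SDs of baseline, follow-up and change.

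- Controls: r = (1.71² + 1.98² − 1.97²) / (2 × 1.71 × 1.98) = 0.44; b = 0.44 × 1.98 / 1.71 = 0.51; 1 − b = 0.49.
- Programme: r = (1.86² + 1.52² − 2.01²) / (2 × 1.86 × 1.52) = 0.31; b = 0.31 × 1.52 / 1.86 = 0.25; 1 − b = 0.75.

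The control figure lies inside the assumed range and the programme figure just above it. Both include response to treatment, and two A1C values per patient cannot separate that from regression. They do not establish the assumption.

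**5. A second route.** If usual means are equal but a single A1C is less reliable in one group, bias = (difference in reliability) × (baseline mean − usual mean). Take the pilot baseline of about 11.38 (midpoint of 11.35 and 11.41), an assumed usual mean of 8.0 to 9.5, and an assumed reliability gap of 0.10 to 0.20. The result is 0.10 × 1.88 = 0.19 to 0.20 × 3.38 = 0.68. The order of size is similar, but this is a different mechanism with equally assumed inputs, so it does not confirm step 3.

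**6. Against the plan's differences.** At 128 pairs with SD 2 and no true effect, a spurious 0.2 is declared significant in 20% of studies, 0.3 in 39% and 0.5 in 80%. The SAP reports an observed 1.6 with SD 2.25. Taking off the largest value in step 3 leaves 1.6 − 0.70 = 0.9, and t = 0.9 / 2.25 × √128 = 4.5. In the pilot the difference is 3.08 − 1.64 = 1.44, which leaves 0.74.

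**7. What one earlier value buys.** If the transient parts of two readings are independent with equal variance, adjusting for both turns 1 − b = λ into λ / (2 − λ): 0.3 becomes 0.3 / 1.7 = 0.18, and 0.7 becomes 0.7 / 1.3 = 0.54. The range of 0.15 to 0.70 becomes about 0.09 to 0.54. A simulation of the step 5 mechanism (usual mean 9, SD 1.6, transient SD 1.2 in programme patients and 0.8 in controls, no treatment effect, all assumed) gave a spurious −0.25 when matched on baseline alone and −0.14 when also matched on one earlier value. With the SDs swapped, the figures were +0.23 and +0.14.

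**The case against.** The best reply is that nothing shows the groups to differ. Four of the seven high-risk features (systolic pressure, LDL, depression, BMI) say nothing about whether an A1C is transient, and any one of them suffices. Randomly chosen patients with elevated A1C may share them. A1C is by the Protocol's own definition a 2-3 month average, and the exclusions (known DKA history, supraphysiologic glucocorticoids, active cancer, pregnancy) remove several causes of a temporary rise. Selection on a single value is documented for programme patients but not for controls, and matching on baseline A1C is explicit only for the pilot. All of this stands. It makes the bias conditional, without showing that it is absent.

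A reader might infer from the 1.64-point fall in pilot controls that regression is large here and inflates the programme effect. The documents do not support this. That fall is what the control group is there to subtract; it mixes usual care with regression and does not measure any difference in regression between groups. The Protocol's explanation of it is incomplete, but it is background and not an analysis rule.

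A reader might also infer that regression accounts for the reported benefit. It does not on any range shown here. With a usual mean of 8.0 to 9.5, producing the whole 1.6 by the step 5 route needs a reliability gap of 0.47 to 0.85.

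Finally, earlier A1C values may not be in the charts. One visit in 12 months is enough for entry, and it may be the qualifying visit. This limits the remedy but is no reason to leave available values uncollected.

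**Conclusion.** The point holds as a conditional one. The plan has no pre-baseline A1C, so it can neither detect nor reduce regression to the mean that differs between groups whose entry rules are not the same. Over the assumed ranges the bias is 0.15 to 0.70 points, in an unknown direction. That is comparable with the 0.5-point design difference and bears on how large the HbA1c effect is reported to be, rather than on whether there is one. It rests on a common linear slope, on 1 − b of 0.3 to 0.7, and on usual means 0.5 to 1.0 point apart. None of these can be checked from the documents. A cheap improvement worth making.

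**What to change.** - **Data list (Protocol, section III).** For programme patients and controls, add the most recent A1C taken 3 to 15 months before the baseline value, where the chart has one.
- **Description.** Report by group how many patients have this value, and the change from it to baseline.
- **SAP.** Pre-specify an HbA1c mixed model that adjusts for baseline and prior A1C, and report it alongside the unadjusted result whatever the prior-to-baseline change shows. Choosing the main result after seeing that change would be data-driven. The SAP already quotes an observed difference, so if the analysis has been run, label this model as added afterwards.
- **Missing prior values.** Use multiple imputation, or restrict to pairs with a prior value as a sensitivity analysis. A missing-value indicator alone generally leaves bias in a non-randomised comparison. Report newly diagnosed patients separately.

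The cost is one more field in a retrospective chart review, one covariate and one descriptive table. N stays at 128. Prior values will be missing for new diagnoses and some others, perhaps unevenly between groups, and one earlier value reduces the bias without removing it.
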